7.4.5. Best Overall Response

Best overall response for each subject is defined as best response during the course of the study (best in the categories of CR, VGPR, or PR), including responses at unscheduled visits.

Subjects without a BOR (ie, subjects not achieving a response of either CR, VGPR, or PR) in the treatment phase will be considered as nonresponders for BOR in the responder analysis. Number and percentage of subjects in each best response category will be tabulated by treatment group in the FAS.

7.4.6. Time to Response

Time to response is defined as time from randomization to the first response of either CR, VGPR, or PR before initiation of new anti-GVHD therapy. In the TTR analysis, subjects without a response after randomization will be censored at either study withdrawal, initiation of new, systemic anti-GVHD therapy, death, or last response assessment prior to or on the cutoff date, whichever is earliest.

The KM curves; medians; 1-, 2-, 6-, 12-, 18-, and 24-month (at Days 30, 60, 180, 365, 547, and 730, respectively) survival estimates, and 95% CIs will be estimated (Brookmeyer and Crowley 1982).

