## 2. STUDY OBJECTIVES AND ENDPOINTS

Primary Objective	Primary Endpoint
Compare the efficacy of itacitinib in combination with corticosteroids versus placebo in combination with corticosteroids in terms of ORR at Day 28 in subjects with aGVHD.	ORR at Day 28, defined as the proportion of subjects demonstrating a CR, VGPR, or PR.
Key Secondary Objective	Key Secondary Endpoint
Compare the efficacy between treatment cohorts at a subsequent key clinical landmark.	NRM at Month 6, defined as the proportion of subjects who died due to causes other than malignancy relapse at Month 6.
Secondary Objectives	Secondary Endpoints
Compare additional response and longer-term efficacy outcomes between treatment cohorts.	ORR, defined as the proportion of subjects demonstrating a CR, VGPR, or PR at Days 14, 56, and 100.
	NRM at Months 9, 12, and 24.
	DOR for responders will be calculated. The DoR is defined from the time of the onset of response to loss of response. Subjects who died or discontinued will be censored at the death date or the previous assessment.
	TTR, defined as the interval from treatment initiation to first response.
	Relapse rate of malignant and nonmalignant hematologic diseases, defined as the proportion of subjects whose underlying hematologic disease relapses.
	Malignancy relapse-related mortality rate, defined as the proportion of subjects whose malignancy relapses and has a fatal outcome.
	FFS, defined as the proportion of subjects who are still alive, have not relapsed, have not required additional therapy for aGVHD, and have not demonstrated signs or symptoms of cGVHD, at Month 6.
	OS, defined as the interval from study enrollment to death due to any cause.
Assess the incidence and severity of AEs and SAEs.	Clinical safety data (eg. AEs, infections) will be tabulated and listed.
Evaluate the PK of itacitinib when administered in combination with corticosteroids.	$C_{max}$ , $C_{min}$ , $t_{max}$ , AUC, and CL/F.
Evaluate the incidence of secondary graft failure.	Incidence rate of secondary graft failure, defined as > 95% recipient cells any time after engraftment with no signs of relapse, OR retransplantation because of secondary neutropenia ( $< 0.5 \times 10^9/L$ ) and/or thrombocytopenia ( $< 20 \times 10^9/L$ ) within 2 months of transplant.

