7.3.1. Primary Efficacy Analysis

7.3.1.1. Day 28 Overall Response Rate

The primary efficacy endpoint, ORR at Day 28 (ie, with either a CR, VGPR, or PR at Day 28 assessment or other response assessments within 3 days of Day 28, before start of new anti-GVHD therapy), will be analyzed using a stratified CMH test. Note that the EOT visit must be accounted for in the Day 28 ORR calculation, because when the EOT and Day 28 visits occur at the same time, per protocol, EOT will supersede the Day 28 visit. That is, if the EOT visit occurs when the Day 28 visit is planned, data from the EOT visit will be used in lieu of the Day 28 visit.

Responders ([CIBMTR 2009](#), [Harris et al 2016](#); refer to Protocol Appendix B):

- (CR) Complete response
- (VGPR) Very good partial response
- (PR) Partial response

Non-responders:

- (MR) Mixed response
- (PD) Progression of disease
- (NR) No response
- (NA) Not applicable
- Other
- Missing (primary reason)
 - Death prior to the Day 28 visit
 - Withdrawal from study prior to the Day 28 visit
 - Initiation of new anti-GVHD therapy prior to the Day 28 visit
 - Missing visit

Day 28 ORR will be summarized using descriptive statistics (N, %) by treatment group with 2-sided exact binomial 95% CIs. P-value, mean proportion difference, odds ratio, and 95% Wald confidence limits calculated from stratified CMH test will be also presented.

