7.4.3. Competing-Risks Analyses of Nonrelapse Mortality

In the literature, analyzing NRM is normally conducted in the context of a competing-risks situation. Time from randomization to first occurrence of NRM or competing event is observed and used for analysis; otherwise, the subject is censored. Nonrelapse mortality and a competing-risk event are mutually exclusive. This is because a subject either dies due to malignancy relapse, dies due to an event other than malignancy relapse, or is censored at last follow-up. There are 2 types of competing-risks analyses:

- I: Time to NRM competing with time to malignancy relapse
Time to first occurrence of either death due to reasons other than malignancy relapse (NRM) or malignancy relapse is defined as an event of interest and competing risk event, respectively. Subjects without an event (neither event of interest nor competing event) will be censored at the date of study withdrawal or date of last contact before or on the cutoff date, whichever is the earlier.
- II: Time to NRM competing with time to death due to malignancy relapse
Time to first occurrence of either death due to reasons other than malignancy relapse (NRM) or death due to malignancy relapse is defined as an event of interest and competing risk event, respectively. Subjects without an event (neither event of interest nor competing event) will be censored at the date of study withdrawal or date of last contact before or on the cutoff date, whichever is the earlier.

For each of the competing-risks analyses (ie, I and II), there are 2 ways of modeling conducted in this study. The first one is cause-specific hazard modeling and the second one is subdistribution hazard modeling.

In cause-specific hazard modeling, competing events will be censored, and a stratified log-rank test [REDACTED] will be used to test 2 KM curves with KMC estimate equals 1 minus KM estimate. In cause-specific hazard modeling, stratified Cox regression model [REDACTED] with a cofactor of treatment group will be used to estimate cause-specific hazard ratio (itacitinib vs placebo) and 95% CI.

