$$H_{02}: \theta_2 \geq 1 \text{ versus } H_{A2}: \theta_2 < 1$$

where θ_2 is the OS hazard ratio (treatment versus placebo). The analysis to test these hypotheses will consist of a stratified log-rank test at an overall 1-sided 2.5% level of significance. The stratification will be based on the randomization stratification factors (ie, aGVHD high vs standard).

The stratified log-rank test adjusting for the strata used in the randomization will be implemented as follows: In each of the K strata separately, the LIFETEST procedure with **STRATA** statement including only the treatment group variable and with the TIME statement will be used to obtain the rank statistic S_k and variance $\text{var}(S_k)$ where $k=1, 2, \dots, K$. The final test statistics will then be reconstructed as follows:

$Z = [S_1 + \dots + S_K] / \sqrt{[\text{var}(S_1) + \dots + \text{var}(S_k)]}$. One-sided P-value will be obtained from the standard normal distribution using the Z statistic.

(One-sided will be obtained using Z statistic / Two-sided p-value will be obtained using Z^2 statistic.)

Kaplan-Meier Estimates

An estimate of the OS survival function in each treatment group at distinct event times will be constructed using KM (product-limit) method as implemented in PROC LIFETEST with METHOD=KM option. The PROC LIFETEST statement will use the option CONFTYPE=LOGLOG. Stratification factor (high vs standard) will be use in **STRATA** statement to get KM estimates by both treatment group and stratum.

Median survival for each treatment group will be obtained along with 95% CIs calculated from PROC LIFETEST output using the method of ([Brookmeyer and Crowley 1982](#)). Kaplan-Meier estimates of the survival function with 95% CIs at specific time points will be summarized. The standard error of the KM estimate will be calculated using Greenwood's formula ([Collett 1994](#)).

Hazard Ratio

Hazard ratio will be estimated by fitting the Cox proportional hazards model using SAS procedure PHREG.

A stratified unadjusted Cox model will be, that is, the MODEL statement will include the treatment group variable as the only covariate and the **STRATA** statement will include stratification variable(s).

Hazard ratio with 2-sided 95% CI will be based on Wald test.

The above survival analyses (ie, log-rank test, KM method and Cox proportional hazards model) do not consider competing risk to be an issue.

Table No.	Title	Population	Standard	In-Text

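### Kaplan-Meier time to response censors death and new anti-GVHD therapy, so it overstates the probability of response and can distort the arm difference in either direction

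*SAP*

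**What the plan says.** SAP 7.4.6 defines the event narrowly: "Time to response is defined as time from randomization to the first response of either CR, VGPR, or PR before initiation of new anti-GVHD therapy". The censoring rule is that "subjects without a response after randomization will be censored at either study withdrawal, initiation of new, systemic anti-GVHD therapy, death, or last response assessment" up to the data cutoff, whichever comes first. The output is "The KM curves; medians; 1-, 2-, 6-, 12-, 18-, and 24-month" estimates with 95% CIs. No cumulative incidence of response is planned, and no test, hazard ratio or arm difference is named. Protocol 9.4.2 gives only a definition for this endpoint.

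Elsewhere the SAP handles the same events differently:

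- **Day 28 ORR (SAP 7.3.1.1).** The non-responder categories include "Death prior to the Day 28 visit" and new therapy started before that visit. These subjects stay in the denominator.
- **Best overall response (SAP 7.4.5).** Subjects who never respond count as non-responders.
- **NRM (SAP 7.4.3).** The SAP writes "In the literature, analyzing NRM is normally conducted in the context of a competing-risks situation" and plans cumulative incidence, Gray's test and Fine-Gray regression.
- **General survival methods (SAP Appendix A).** The log-rank, Kaplan-Meier and Cox analyses "do not consider competing risk to be an issue".

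The time origin also differs. Protocol Section 2 has "TTR, defined as the interval from treatment initiation to first response", and SAP Table 1 repeats it, but SAP 7.4.6 starts the clock at randomization. SAP 10.1, on changes to protocol-defined analyses, does not mention this.

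**The concern.** Kaplan-Meier censoring assumes that a censored subject could still have the event later, at the rate seen in those who remain at risk. That is tenable for a subject who is event-free at the data cutoff. It cannot hold for a subject who has died, or for one who has started new therapy, because the definition then bars a response. The estimator spreads these subjects' probability over the later responders, so 1-KM is too high as a probability of response. The Kaplan-Meier median, being the time when 1-KM reaches 50%, cannot fall later than the time when the cumulative incidence reaches 50%.

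Time to response is a named secondary endpoint under an objective to compare the arms. Its landmark estimates will be read as the proportion who had responded by each time. They would sit in the same report as a best overall response rate that counts the same subjects as failures.

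**Working it through.** **Inputs from the documents.** Day 28 response is planned at 56% (placebo) vs 72% (itacitinib), with stratum rates of 68%/44% vs 81%/61%, a 50:50 risk split, 207 per arm and about 90% power at one-sided 0.025 (SAP 3.3). No figure is stated for time to response, and no rate of death or new therapy before response appears anywhere.

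**Check on the planning rates.** A normal-approximation CMH power for two strata of 103.5 per arm uses:
- weight 103.5²/207 = 51.75 per stratum;
- numerator 51.75 × (0.13 + 0.17) = 15.525;
- null SD 4.768 and alternative SD 4.706.

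Power = Φ((15.525 − 1.96 × 4.768)/4.706) = 0.905, or 0.886 with continuity correction. The stated 90% is reproduced, so 56% vs 72% is a sound base for the illustration.

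**Formula.** Let R be the cumulative incidence of first response and C that of death or new therapy before response. If the two hazards keep a constant ratio within an arm, the cumulative response hazard is the share R/(R+C) of the total −ln(1−R−C). Hence

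1-KM = 1 − (1−R−C)^(R/(R+C)), while the true probability is R.

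**Assumptions.** Day 28 ORR is taken as the cumulative incidence of first response, and the values of C are assumed and varied.

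**Worked cases.**
- 10% on placebo: 1 − 0.34^(0.56/0.66) = 60.0%. 5% on itacitinib: 1 − 0.23^(0.72/0.77) = 74.7%.
- 30% on placebo: 1 − 0.14^(0.56/0.86) = 72.2%. 15% on itacitinib: 1 − 0.13^(0.72/0.87) = 81.5%.
- 15% on placebo: 1 − 0.29^(0.56/0.71) = 62.3%. 12% on itacitinib: 1 − 0.16^(0.72/0.84) = 79.2%.

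| Assumed failures before response, placebo/itacitinib | 1-KM placebo | 1-KM itacitinib | Overstatement (points) | Difference (true 16.0) |
|---|---|---|---|---|
| 10% / 5% | 60.0% | 74.7% | 4.0 / 2.7 | 14.7 |
| 20% / 10% | 65.1% | 77.8% | 9.1 / 5.8 | 12.8 |
| 30% / 15% | 72.2% | 81.5% | 16.2 / 9.5 | 9.3 |
| 15% / 12% | 62.3% | 79.2% | 6.3 / 7.2 | 16.9 |
| 15% / 15% | 62.3% | 81.5% | 6.3 / 9.5 | 19.2 |

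Differences were taken before rounding.

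**Break-even.** The 16-point difference is preserved when itacitinib failures are 7.1% against 10% on placebo, 14.4% against 20%, or 21.8% against 30%. The ratio is about 0.71 to 0.73. Below it the difference shrinks; above it the difference widens.

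**Cross-check without constant hazards.** A weekly-visit model assumed response probabilities per visit of 0.25 then 0.08 then 0.03 (placebo) and 0.38 then 0.12 then 0.05 (itacitinib), for weeks 1–2, weeks 3–4 and later.
- Weekly failure risk 6% vs 3%: the difference goes from a true 19.8 to 17.8 points at week 4, and from 23.1 to 14.7 at week 26.
- Equal 5% risk: it goes from 16.7 to 17.8 at week 4, and from 15.5 to 14.7 at week 26.
- Failures starting only after week 4: no bias at week 4.

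**The case against.** The strongest reply is that little depends on this endpoint. SAP 3.2 leaves it outside the alpha-controlled tests, no comparison is planned in SAP 7.4.6 or Protocol 9.4.2, and the response proportions that carry the efficacy claim already count failures as non-responders. All of that stands, and it limits the consequence. It does not make the estimates right. The Appendix A remark on competing risk does not rescue them either: that text takes overall survival as its example, where no competing event exists.

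A cause-specific analysis that censors these events is also legitimate if it is read as a statement about the response rate among those still at risk. That is correct, but SAP 7.4.6 does not label its curves and landmark estimates that way.

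Four stronger readings are tempting, and the documents do not support them:

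- **The bias is largest in the arm with more failures and so shrinks the difference.** It depends on response and failure hazards jointly. At 15%/12%, placebo has more failures but the smaller overstatement, and the difference widens.
- **A large, fixed shrinkage.** If 90% of each arm is resolved, with response-to-failure hazard ratios of 2:1 and 4:1, true rates of 60.0% vs 72.0% appear as 78.5% vs 84.2%, so 12 points become 5.7. That is one assumed scenario with failures of 30% vs 18%, on the shrinking side of break-even. None of its inputs comes from the documents.
- **Late estimates drift towards 100%.** This needs first responses to keep occurring late. Protocol 1.4.2 reports that most Phase 1 responses came in the first 14 days, and with few late responses the curve would plateau.
- **The estimates should match ORR at Days 14, 56, 100 and 180.** Those are response status at a visit (SAP 7.4.4). A cumulative incidence of first response would not equal them either. Best overall response is the nearer comparator.

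**Conclusion.** The concern holds as an estimator error in a descriptive secondary endpoint. Under SAP 7.4.6, 1-KM overstates the cumulative probability of response in any arm where death or new systemic anti-GVHD therapy precedes later responses. At the planning rates, the overstatement across the five scenarios runs from 2.7 to 16.2 points per arm, and a true 16-point difference appears as anything from 9.3 to 19.2. These sizes rest on assumed failure rates, on a constant ratio of response to failure hazards, and on using Day 28 ORR as cumulative incidence of first response. The overstatement itself rests only on the definition and the censoring rule. The direction of the effect on the arm difference cannot be stated in advance.

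The inconsistent time origin is real but minor: Protocol 6.1 has treatment start within 2 days of randomization, so the shift is at most about 2 days. The primary and key secondary analyses and best overall response are untouched.

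**What to change.** In SAP 7.4.6, replace the Kaplan-Meier estimates with the cumulative incidence of first response, treating death and new systemic anti-GVHD therapy before response as competing events. Keep censoring for study withdrawal and for subjects still event-free at their last assessment. Give the median time to response among responders as a descriptive summary. If any cause-specific analysis is retained, label it as such. Choose one time origin and use it in the protocol, SAP Table 1 and SAP 7.4.6; if it stays at randomization, record the change in SAP 10.1.

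Stratified Gray's test and the choice of landmark days are optional, since no comparison is planned now.

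The cost is SAP wording and reuse of the cumulative incidence methods already specified in SAP 7.4.3. The downside for the sponsor is that the reported response probabilities become lower.

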7.4.7. Relapse Rate of Malignant and Nonmalignant Hematologic Diseases

Relapse rate of malignant and nonmalignant hematologic diseases is defined as the proportion of subjects whose underlying hematologic diseases relapse. Incidence of such events will be tabulated with summary statistics.

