## 1. INTRODUCTION

### 1.1. Overview of Acute Graft-Versus-Host Disease

Allogeneic HSCT is an effective immunotherapy for human cancer ([Appelbaum 2007](#)). More than 32,000 allo-HSCTs are performed each year worldwide, primarily for the treatment of hematologic malignancies ([Niederwieser et al 2016](#)). Acute GVHD and cGVHD remain major contributors to transplantation-related deaths and the most significant barrier to successful allo-HSCT. GVHD occurs when donor-derived immune cells recognize the transplant recipient (the host) as foreign, thereby initiating an immune reaction and subsequent inflammatory cascade that results in varying degrees of tissue damage and potential organ failure in the transplant recipient. Despite prophylactic treatments with immunosuppressive agents, approximately 50% of transplantation recipients develop GVHD. Risk factors associated with aGVHD include donor/recipient HLA mismatch, increased age (donor or recipient), sex, intensity of the pretransplant conditioning regimen, and donor source ([Jagasia et al 2012](#), [Flowers et al 2011](#)). Most GVH reactions are undesirable and affect multiple organs; however, GVH reactions against hematopoietic tissue targets are desirable and critical for the cure of hematologic malignancies (ie, the GVT effect) and for donor immune-hematopoietic system engraftment. These disparate effects of GVH reactions are difficult to separate, and any strategies directed against GVHD may adversely affect survival by increasing malignancy relapse, graft rejection, and the frequency and severity of infections ([Pavletic and Fowler 2012](#)).

There are few therapeutic studies for aGVHD, and currently no agents are approved by the FDA for either prevention or treatment of aGVHD ([Martin et al 2009](#)). At diagnosis, the extent of individual organ involvement and overall grade of aGVHD should be documented, taking into account all organ involvement, as this has prognostic significance. Acute GVHD diagnosis should be confirmed by biopsy of an affected organ if possible; in addition, other non-GVHD complications involving the skin, liver, and GI tract should be ruled out. Although diagnostic biopsies are highly specific if current histopathology criteria are used, the sensitivity of these biopsies is only approximately 60%; therefore, the ultimate aGVHD diagnosis and decision to treat systemically is based on careful integration of all available clinical information ([Weisdorf et al 2003](#)).

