#### 9.4.2. Secondary Analyses

The key secondary endpoint is NRM at Month 6, defined as the proportion of subjects who died due to causes other than malignancy relapse at Month 6. The comparison of NRM at Month 6 between treatment cohorts will be conducted using a 2-sample proportion test with normal approximation. Summary statistics and 95% CI will be provided.

Additional secondary endpoints will be analyzed as follows:

- ORR, defined as the proportion of subjects demonstrating a CR, VGPR, or PR at Days 14, 56, and 100. The comparison between treatment cohorts will be conducted using a 2-sample proportion test with normal approximation. Summary statistics and applicable 95% CI will be provided.
- NRM, defined as the proportion of subjects who died due to causes other than malignancy relapse at Months 9, 12, and 24. The comparison between treatment cohorts will be conducted using a 2-sample proportion test with normal approximation. Cumulative incidence rates will be provided. Summary statistics and applicable 95% CI will be provided.
- DOR, defined as the time from first response until GVHD progression or death. The comparison between treatment cohorts will be conducted using the log-rank test. The Kaplan-Meier method will be used. Summary statistics will be provided.
- TTR, defined as the interval from treatment initiation to first response.
- Relapse rate of malignant and nonmalignant hematologic diseases, defined as the proportion of subjects whose underlying disease relapses. The comparison between treatment cohorts will be conducted using a 2-sample proportion test with normal approximation. The cumulative incidence rate and summary statistics will be provided.

- Relapse-related mortality rate, defined as the proportion of subjects whose malignancy relapses and has a fatal outcome. The comparison between treatment cohorts will be conducted using a 2-sample proportion test with normal approximation. The cumulative incidence rate and summary statistics will be provided.
- FFS, defined as the proportion of subjects who are still alive, have not relapsed, have not required additional therapy for aGVHD, and have not demonstrated signs or symptoms of cGVHD, at Month 6. The comparison between treatment cohorts will be conducted using the log-rank test. The Kaplan-Meier method will be used. Summary statistics will be provided.

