5.3.3. Final Analysis

All efficacy analyses and demographic and baseline summaries will be presented by planned treatment group, that is, by either itacitinib or placebo.

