7.4.8. Malignancy Relapse-Related Mortality Rate

Malignancy relapse-related mortality rate is defined as the proportion of subjects whose malignancies relapse and have a fatal outcome. Incidence of such events will be tabulated with summary statistics.

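### SAP 7.4.7 and 7.4.8 analyse relapse and relapse mortality only as crude proportions, without the comparison and cumulative incidence promised in Protocol 9.4.2; these mix any relapse effect with the expected NRM effect

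*SAP*

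**What the plan says.** SAP 7.4.7: "Relapse rate of malignant and nonmalignant hematologic diseases is defined as the proportion of subjects whose underlying hematologic diseases relapse". SAP 7.4.8: "Malignancy relapse-related mortality rate is defined as the proportion of subjects whose malignancies relapse and have a fatal outcome". Each section then gives one analysis sentence: "Incidence of such events will be tabulated with summary statistics". Neither names a landmark, a censoring rule, a test, a hazard ratio or a cumulative incidence estimate.

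Protocol 9.4.2 goes further for both endpoints: "The comparison between treatment cohorts will be conducted using a 2-sample proportion test with normal approximation", and "The cumulative incidence rate and summary statistics will be provided". It sets no time point either. SAP 10.1, which lists changes to Protocol-defined analyses, contains only a note on the naming of the full analysis set.

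SAP 7.4.3 does specify cause-specific and subdistribution models, but with NRM as the event of interest. Relapse enters only as the competing event, as in "I: Time to NRM competing with time to malignancy relapse". SAP 5.3.3 provides display by arm: "All efficacy analyses and demographic and baseline summaries will be presented by planned treatment group, that is, by either itacitinib or placebo".

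**The concern.** Protocol 1.1 names relapse as a possible cost of the treatment strategy: "any strategies directed against GVHD may adversely affect survival by increasing malignancy relapse". The relapse endpoints are where a reader will look for that cost.

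Two features make a crude proportion hard to read.

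- **Unequal follow-up.** The final analysis takes place when the last subject reaches Day 180 or withdraws (SAP 3), so follow-up runs from about six months upward. At Interim 2 the efficacy set admits subjects who have just completed Day 28 (SAP 5.3.2.1), and it replaces the full analysis set if the study stops there (SAP 6). The two interim cutoffs, 25 JUN 2018 and 17 APR 2019, are 296 days apart. An early subject still in follow-up could therefore have about 28 + 296 = 324 days, against about 28 for a late one. The resulting proportion refers to no particular time.
- **Competing deaths.** A subject who dies without relapse can no longer relapse. The plan expects many fewer such deaths on itacitinib, which leaves more subjects able to relapse. A drug with no effect on relapse would then show more relapses, and a true effect would be mixed with this one.

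**Working it through.** **Inputs from the documents.** NRM at Month 6 is 33% on control and 19.8% on itacitinib (Protocol 9.2, SAP 3.3), with 218 subjects per arm randomized.

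**The plan's own figure.** Protocol 9.2 states 83% power for NRM with 207 per arm at one-sided 0.025. A normal approximation to the two-stratum CMH test, using 22%/44% v 12.4%/28.2%, gives 82.2% with continuity correction and 85.1% without. The stated figure is reproduced closely enough, and this point does not dispute it.

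**Assumption.** The documents give no planning relapse rate. I take a relapse hazard r = 0.025 per month, identical in both arms, with range 0.015 to 0.035.

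**Formulas (time T in months).**

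- NRM hazard: n = -ln(1 - p)/6. Placebo: -ln(0.67)/6 = 0.0667. Itacitinib: -ln(0.802)/6 = 0.0368.
- If the NRM hazards persist, proportion relapsed by T = r/(r+n) × (1 - exp(-T(r+n))).
- If NRM stops at Month 6, for T > 6: the Month 6 value + exp(-6(r+n)) × (1 - exp(-r(T-6))).

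**Example, Month 6.** Placebo: 0.025/0.0917 × (1 - exp(-0.5505)) = 11.5%. Itacitinib: 0.025/0.0618 × (1 - exp(-0.3706)) = 12.5%.

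| Month | NRM after Month 6 | Placebo | Itacitinib | Excess, points (range over r) |
|---|---|---|---|---|
| 6 | not applicable | 11.5% | 12.5% | +1.0 (+0.6 to +1.4) |
| 12 | stops | 19.6% | 22.2% | +2.6 (+1.7 to +3.4) |
| 12 | persists | 18.2% | 21.2% | +3.0 (+1.9 to +3.9) |
| 24 | stops | 32.4% | 37.6% | +5.1 (+3.5 to +6.4) |
| 24 | persists | 24.2% | 31.3% | +7.0 (+4.8 to +8.6) |

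Excesses are taken from unrounded values. The drug has no effect on relapse in any row.

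**Sampling error at Month 6.** sqrt[(0.115 × 0.885 + 0.125 × 0.875)/218] is about 3.1 points, so the +1.0 point excess is small beside it.

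**Sensitivity to the model.** The hazards above treat 33% and 19.8% as risks in the absence of relapse. With r = 0.025 the model's Month 6 NRM proportions are 30.8% and 18.4%. Solving instead for hazards that return exactly 33% and 19.8%, with placebo relapse at Month 6 assumed anywhere from 5% to 40%, gives an excess of +0.5 to +4.7 points at Month 6. At Month 24 it gives +3.6 to +13.7 if the hazards persist. The direction is the same throughout.

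**What separates the two effects.** With complete follow-up, the formula above is the cumulative incidence function itself. Cumulative incidence would therefore show the same gaps, and Gray's test would test them. In a simulation of 400,000 subjects per arm (15% assumed placebo relapse at Month 6), the crude proportions at 24 months were 29.0% v 37.9%, while the cause-specific hazard ratio for relapse was 1.00.

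**The case against.** **Relapse is informed elsewhere.** It is a component of failure-free survival, which has Kaplan-Meier estimates to 24 months, a stratified log-rank test and a Cox model (SAP 7.4.9). Overall survival is compared by arm (SAP 7.4.10). Appendix B includes a relapse summary table and a relapse listing. SAP 3.2 promises 95% confidence intervals for other endpoints. A reader might infer that the SAP leaves no means of seeing relapse harm. The documents do not support that: display by arm remains, and what is missing is a time-anchored estimate and a formal comparison of relapse itself.

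**The promised analyses would not cure the problem.** A reader might infer that the artefact comes from dropping the Protocol's proportion test and cumulative incidence. It does not, since both would show the same excess. Their loss matters because they were promised, and because cumulative incidence handles unequal follow-up and fixes the time point.

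**The larger figures extrapolate.** The plan gives NRM rates only to Month 6. Persisting hazards imply NRM of about 65% v 46% by Month 24 with r = 0.025, which nothing in the documents supports. This objection stands, so the Month 24 figure of +7.0 should not be read as a forecast.

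**Unequal follow-up is not itself a bias.** Under 1:1 randomization it should be similar in the two arms. It harms interpretation and does not by itself favor an arm.

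**Silence is not withdrawal.** SAP 10.1 does not say that the comparison was dropped. A deliberate removal might be inferred, but the text shows only an unreconciled difference. The supplied SAP also lacks or redacts parts of Appendix B and of sections 7.5 and 7.6, so an unseen relapse incidence table cannot be excluded. The readable text specifies none.

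**Conclusion.** The concern holds in a limited form. The two SAP sections fall short of Protocol 9.4.2, the difference is not recorded, and a crude proportion cannot distinguish a relapse effect from the NRM effect that the trial is designed to find.

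The distortion is about one point at Month 6, the only time covered by the plan's NRM rates, and too small to mislead much there. It grows with follow-up to about 3 points at Month 12 and 5 to 7 at Month 24, depending on later NRM. These sizes rest on an assumed relapse hazard, equal in the two arms, and on constant hazards over each period. The direction follows whenever NRM is lower on itacitinib and the relapse hazard is unchanged.

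The cause-specific hazard ratio separates the two effects under this model. If subjects spared from NRM carry a different relapse risk, it will reflect that too, so it should be read together with cumulative incidence and NRM. These are secondary endpoints without multiplicity adjustment. The change is worth making, but it does not affect the primary or key secondary claim.

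**What to change.** - In SAP 7.4.7 and 7.4.8, make the arm comparison the cause-specific hazard ratio with 95% CI, stratified by GVHD risk status, for relapse and for relapse death. Censor at death from other causes, and state the remaining censoring dates as in SAP 7.4.3.
- Beside it, report descriptively the cumulative incidence of each event by arm at Months 6, 12 and 24, with 95% CI and death from other causes as the competing event. State that it is to be read together with NRM.
- Record the departure from Protocol 9.4.2 in SAP 10.1, with the reason.

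The cost is SAP wording and reuse of the SAP 7.4.3 programs with the event codes swapped. Relapse is assessed through survival follow-up (Protocol Table 3), and its timing is already needed for failure-free survival and for the first competing-risks analysis, so no new data are required.
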